2.3. Secondary Objectives

To investigate the neuroplasticity in the brain through multiple neuro-imaging analysis (fMRI/MRI/DTI), with the goal to develop imaging biomarkers for image-guided neuro-rehabilitation framework so as to optimize early UL practice after stroke.

2.4. Potential Risks and benefits:

a. End Points - Efficacy

SURE program improves UL functional outcome and influences neuroplasticity positively to optimize UL recovery after stroke.

b. End Points - Safety

SURE Program

Subjects might experience fatigue at the early part of the exercise program.

The CPI will tailor and review subjects' exercises and the use of stroke-affected hand in daily tasks according subjects' stroke-affected hand's capability.

The CPI will consult the treating rehabilitation team (including doctors, therapists, nurses) on the subjects' medical and neurological stability before the commencement of teaching the exercises and each review.

First session of teaching exercises

CPI will pause, observe and ask each subject after teaching each exercise if they are tired. If they are tired, the CPI will stop teaching and let the subjects rest until they are not tired and ready to learn the next exercise. If the subjects are observed or express tiredness, the CPI will stop teaching the exercises for that session. Subjects will be advised to stop doing their exercises if they feel tired or rest until they feel ready to continue to do the exercises. The caregivers who are assisting the subjects with self-exercises will be given the similar advice. Subjects will also be asked to record any pain or fatigue that they experience during performance of self-exercises in their Exercise Log.

The next day after the first session

CPI will check the subjects' performance of their exercises and their level of tiredness, and also to reinforce the advice to rest if they are feeling tired.

Subsequent reviews

CPI will check the subjects' performance of their exercises and their level of tiredness, and also to reinforce the advice to rest if they are feeling tired.

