Doctors, therapists and nurses who are taking care of the subjects in TTSRHC will be informed of the subjects' participation in SURE program and will be kindly requested to keep a look out of any verbal and non-verbal expressions of fatigue by the subjects. They will be informed to give similar advice by CPI to stop exercise and rest before continually or stop the exercises entirely if the subjects are too tired on that particular day. CPI will be informed by the treating team of their findings and will continue to monitor the subjects' suitability to continue with SURE program if there are reports of persistent fatigue due to self-exercises in the ward. Additional monitoring of fatigue level will be performed at pre, 2 weeks of intervention, post-intervention assessment using the Stanford Fatigue Scale.

A possible minimal risk is the development of allergy to the straps of the sensors. However, many research studies had used the sensors and there have been no reports of any adverse allergic reactions or problems reported with wearing the sensors.

Transcranial Magnetic Stimulation (TMS) Screening

TMS safety parameters have been documented and stimulation guidelines have been established (Wasserman, 1998). Seizures are the most important potential adverse event but are extremely rare. Mild headache, neck pain and discomfort from facial twitches are the most common and resolve spontaneously shortly after stimulation.

Exclusion criteria include pregnancy, presence of cardiac pacemakers, orthodontics (braces), metal implant and intracranial implants such as ventriculoperitoneal shunts and clips.

Functional Magnetic Resonance Imaging Investigation

Magnetic Resonance Imaging use radio waves similar to those used in radio and TV transmission. These have a much lower energy than X rays and are considered biologically safe. We follow strict safety guidelines which are designed to prevent the possible hazards of MRI: burns and electric shocks. The main risk in MRI is injury or death arising from the action of the strong magnetic field on any metal objects on or within the body. This may result in flying metal objects or damage to tissue. Strict screening procedures to remove external metal objects and exclude unsuitable volunteers will be carried out.

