The subjects will be asked to perform the exercises 60 minutes (3x 10- 20 minutes) distributed across morning, afternoon, and evening per day for 6 days per week during the 4-week intervention period. They will also be asked to perform the functional tasks as and when is required for their daily function for 6 days per week during the 4-week intervention period. The subjects will be given an Exercise Log to tick and track number of repetitions of the exercises and functional activities each day, the number of days the protocol is completed, and the level of fatigue and pain experienced. If the subject is discharged from the hospital before the 4 weeks of intervention period, he/ she has to carry on with the protocol till the intervention period ends. The CPI will continue to review exercises and the amount of affected UL use with the subjects at home if the subjects are discharged till the intervention period ends.

Control Group

The control group will receive an education booklet with 10 modules. The education booklet will contain information on stroke, recovery and management strategies after stroke. Subjects are to complete 2-3 modules per week and answer 1-2 simple questions after each module. Each module including answering questions takes approximately 5-10 minutes to complete. The CPI will review the information with the subjects 3 times per week for the first 2 weeks, two times for the third week and one time for the fourth week of intervention period.

Both groups will continue with their daily routine therapy sessions in the hospital. The treating therapists will record the duration of therapy of each subject per day.

UL functional outcome measures- ULM and ARAT will be assessed pre-intervention, 2 weeks after start of intervention, post-intervention, 1month and 3months post-intervention. Measures of **SURE** program's feasibility such as VAS pain score, fatigue level, and MAS of biceps and finger flexors will be measured pre-intervention, 2 weeks after start of intervention and post-intervention. A team member who is blinded to which group the subjects are in will perform the outcome measure assessments.

Multimodal imaging for the normal healthy control will be performed once to establish the activation pattern in normal. Multimodal imaging assessment for the patient subjects will be done pre-intervention, post-intervention, and 3months post-intervention.

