5.1. Summary of Study Design

The subjects will be randomly assigned to a control (N=10) and experimental group (N=10). The control group will undergo an education program while the experimental group will undergo the **SURE** program. Clinical assessments for both groups will be performed by a blinded assessor at pre, two weeks after start of intervention, immediate post intervention, 1 and 3months post-intervention to determine if the **SURE** program improve affected UL functional outcomes compared with the control group. fMRI investigations will be performed at pre-intervention, post- intervention and 3months post-intervention to determine if the increased UL activity in the **SURE** program influences brain neuroplasticity positively early post-stroke.

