Subjects' fatigue levels will be assessed using 0-10 point Stanford Fatigue Visual Numeric Scale (Stanford Patient Education Research Centre, n.d). Subjects' level of affected UL pain will be assessed using 0-10 rating Visual Analogue Scale (VAS). Subjects' UL spasticity level for biceps and finger flexors will be assessed using Modified Ashworth Scale (MAS). These assessments will be performed pre, 2 weeks in training, and post-training.

SURE program feasibility is also assessed by the compliance rate, dropout rate and any adverse events reported during the intervention period.

Subjects and their caregiver will be asked to fill up a questionnaire to rate on **SURE** program's ease, benefit and overall satisfaction based on VAS (rating 0 -10). In addition, 10 nurses in the ward who have taken care of the stroke patients undergoing the **SURE** program in the ward will also be asked to fill up a questionnaire to rate the ease, difficulty, advantages and disadvantages on **SURE** program implementation in the ward.

TMS Screening

A research staff will apply TMS to the subject. The subject will be seated comfortably and instructed to remain as still as he/ she can. A tight swim cap will be worn by the subject. The vertex will be marked on the cap. Single pulse TMS was delivered using a single Magstim 200 via the coil of figure of eight. The coil position was maintained manually by the assistant and the handle of the coil point to posterior with an angle of 45 degree to the sagittal plane. Surface electromyography (EMG) electrodes are attached to the extensor carpi radialis (ECR) for EMG recording. The "hot spot" of the motor evoked potential (MEP) from ECR is first identified and marked for affected side. This spot will be used for all recordings on that side. The subject will

be considered MEP positive if more than or equal 50 μ V amplitude can be elicited in 50% of 10 successive trials while the muscle is at rest. If this criterion is not met with stimuli delivered at maximal intensity, the subject will be considered MEP negative.

Multimodal MRI imaging and Analysis

MRI data acquisition

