11.2. Statistical and Analytical Plans

a. Study Statistical Analysis

Statistical analysis will be performed using STATA version 10.0 for Windows (StataCorp, TX, USA). Descriptive statistics will be used to describe subjects' demographics in each group.

Analysis of UL Functional Outcome

Wilcoxon signed-ranked tests will be used at each time points (pre, 2 weeks after start of intervention, post, 1month post-intervention, 3months post-intervention) to compare UL functional outcomes between the experimental and control groups. The significance level for all statistical tests will be set at $p<0.05$ levels. All data will be analysed by intention to treat.

Analysis of feasibility of accelerometers to measure affected UL use

Analysis of the compliance rate and responses from the questionnaire will be used to determine the feasibility and acceptance of using accelerometers to measure affected UL use after stroke.

Analysis of SURE Program's feasibility

Wilcoxon signed-rank test will also be used to compare outcomes of pain, fatigue and spasticity pre-and post-intervention period. The differences in the duration of affected UL use per day and the ratio of affected UL use/ non-affected UL use between the experimental group and control group (from the accelerometer recordings), the rate of compliance, the proportion of subjects who successfully complete the whole training, and the dropout rate will be calculated to assess the feasibility of **SURE Program**.

Analysis of fMRI investigation

Comparison of activation in primary motor cortex, secondary motor cortex and cerebellar hemisphere for bilateral sides will be done by comparing mean percentage signal change (%SC), absolute voxel counts (VC) and changes in geometric centers of these areas on both sides¹⁷. In addition, a laterality index (LI) will also be calculated to determine the relative cortical activity. Asymmetry has been found to restore to normal (L=1.0) when the affected hand movement improved after rehabilitation⁴¹.

Analysis of resting state fMRI/DTI

Functional connectivity and tract integrity^{32,38} will be studied by FSL with the normalization method^{39,40}. The secondary degeneration of the brain in the remote region to the primary lesion will also be studied for the sub-groups of subjects with less motor recovery³⁰.

MRS analysis

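### The only test named in 11.2 for pain, fatigue and spasticity is pre versus post: without a control-arm or 2-week comparison, a change cannot be attributed to SURE and a transient rise can be missed

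*Protocol*

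**What the plan says.** Section 11.2, under the analysis of the program's feasibility, states: "Wilcoxon signed-rank test will also be used to compare outcomes of pain, fatigue and spasticity pre-and post-intervention period". No other test is named there for these three outcomes. The sentence does not say whether the test is run within each arm or on both arms together.

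The scales are collected more often than the test uses them. Section 5 says that "MAS of biceps and finger flexors will be measured pre-intervention, 2 weeks after start of intervention and post-intervention", in a sentence that also covers pain and fatigue. Section 6 says of all three: "These assessments will be performed pre, 2 weeks in training, and post-training". Section 2.4 b adds for fatigue: "Additional monitoring of fatigue level will be performed at pre, 2 weeks of intervention, post-intervention assessment using the Stanford Fatigue Scale".

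On timing, section 2.4 b says: "Subjects might experience fatigue at the early part of the exercise program". On who is assessed, section 5.1 says: "Clinical assessments for both groups will be performed by a blinded assessor at pre, two weeks after start of intervention", and continues to the later visits.

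On their role, section 5 introduces these scales as "Measures of SURE program's feasibility such as VAS pain score, fatigue level" and so on, and sections 6 and 11.2 also treat them as feasibility measures. Only fatigue has its scale named under the safety endpoints.

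**The concern.** The trial randomises a control arm and has a blinded assessor, but this analysis uses neither to judge how well SURE is tolerated. Patients are admitted within 21 days of stroke (section 3.3), a period in which symptoms may shift with or without extra exercise. A pre-post change in the SURE arm, or in both arms pooled, mixes any such shift with the effect of the program. A worsening common to both arms could be read as caused by SURE, and a worsening due to SURE could be hidden by natural improvement.

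The timing adds to this. Fatigue is expected early, yet the test uses the first and last readings and skips the one between them. A rise that is present at 2 weeks and gone by 4 weeks does not enter it.

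**Working it through.** **Text side by side**

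| Outcome | Collected at | Comparison named in 11.2 |
|---|---|---|
| UL function | pre, 2 weeks, post, 1 and 3 months | experimental vs control at each time point |
| Accelerometry | during the 4 weeks | experimental vs control |
| Pain, fatigue, spasticity | pre, 2 weeks, post | pre vs post only |

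Arm comparisons are named for the other two outcomes in the same section, so the third row is a stated choice and not general silence.

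**Illustration of size**

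The protocol has no figure to reproduce: section 11.1 justifies 10 per arm by feasible recruitment and gives no SD, effect size or power. Inputs from the protocol are n = 10 per arm (section 3.1) and a significance level of 0.05 (section 11.2; two-sided is assumed). Assumed: normal change scores with SD 1, and the drifts and effects shown. Positive values mean worsening.

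Simulation, 4,000 trials per row. The pre-post columns are the signed-rank test in the SURE arm. The last column is the rank-sum test on change scores between arms.

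| Drift in both arms | SURE effect | Pre-post significant | Pre-post significant as worsening | Between arms significant |
|---|---|---|---|---|
| 0 | 0 | 4% | 2% | 4% |
| +0.5 | 0 | 29% | 29% | 4% |
| +1.0 | 0 | 79% | 79% | 4% |
| -0.5 | +0.5 | 5% | 2% | 16% |
| -1.0 | +1.0 | 5% | 2% | 53% |
| 0 | +1.0 | 78% | 78% | 51% |
| 0 | +1.3 | 94% | 94% | 74% |

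Rows 2 and 3 show the attribution problem. Rows 4 and 5 show masking; their 5% follows from assuming that drift and harm cancel exactly. Rows 6 and 7 favour the planned test: without drift it detects a lasting worsening more often than the between-arm test.

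Difference detectable with 80% power (normal approximation):
- within one arm: (1.96 + 0.84)/√10 = 0.89 SD
- between arms: (1.96 + 0.84) × √(2/10) = 1.25 SD

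Power between arms by the same approximation, Φ(d/√(2/10) − 1.96), is 20% at d = 0.5, 43% at 0.8 and 61% at 1.0. The rank-sum simulation gives 51% to 53% at 1.0. The half-width of a 95% interval for the difference in mean change is about 1.96 × √(2/10) = 0.88 SD.

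**The case against.** A reader might infer that these scales carry the safety case for SURE and that a harm could not be detected. The documents support neither. The protocol calls the scales feasibility measures, and the safety analysis in 11.2 is daily monitoring of adverse events and complaints, with a quarterly review that can stop the study. A net worsening that lasts to the end is what a pre-post test can find, as the last two rows of the simulation show.

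Nor is early fatigue invisible to the trial. Section 5 has SURE subjects record fatigue and pain in the Exercise Log. Section 2.4 b has the clinical principal investigator (CPI) check tiredness the day after the first session and at each later review, with three reviews a week in the first two weeks (section 5). Ward staff also report fatigue. What remains is that the log is described for the experimental group only, and the CPI knows the allocation (section 8.5). None of these sources gives a blinded comparison of arms.

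The size is hypothetical. No drift is documented for these symptoms; section 1.1 mentions spontaneous recovery only in connection with UL training. Normal scores are also a rough model for Ashworth grades and 0-10 ratings. The percentages are therefore illustrations only.

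This is a pilot, and an analysis plan that is not shown could add the comparison. That is possible, but 11.2 does name an analysis here, and the one named does not use the control arm. Because 11.2 also applies a signed-rank test to the arm comparison of UL function, the sentence could be read as comparing arms at pre and at post. Even so, the arms are unpaired, so a signed-rank test does not fit, and the 2-week reading is still left out.

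**Conclusion.** The point holds in limited form. The named test cannot separate an effect of SURE from change with time since stroke, and it can miss a transient rise at the stage when the protocol expects fatigue. This limits what the trial can say about tolerability from its only standardised, blinded readings of these symptoms. It does not leave the trial without safety monitoring, and it does not make every harm undetectable.

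The size depends on drift that the protocol does not quantify. With none, the planned test loses nothing for a lasting effect; with a common drift of 0.5 to 1.0 SD it would be significant in 29% to 79% of trials with no SURE effect. The conclusion also assumes that the control arm has these scales at the same visits. Section 5.1 supports this by assessing both groups, but it ties those assessments to UL function and does not list the scales.

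**What to change.** In section 11.2, compare change from baseline in fatigue, pain VAS and MAS between arms, at 2 weeks and at post-intervention. Use a rank-sum test, because the arms are unpaired, and give an estimate of the difference with a confidence interval. Keep the pre-post changes as description, by arm. State in section 5 or 6 that the control arm has these scales at the same visits.

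If that is confirmed, the cost is wording only: no new visits, subjects or measurements. The downside is precision. With intervals of roughly ±0.88 SD and about 50% power at an assumed 1.0 SD, only large differences will stand out. The protocol should present the result as estimation and should not read a non-significant difference as evidence that SURE is well tolerated.

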4. TRIAL SCHEDULE

	Clinical Assessments (TTSHRC)/ no. of visit	TMS Screening (NUH)/ no. of visit	fMRI Investigations (CIRC@NUS)/no. of visit
Pre-Intervention	1 (Inpatient)	1 (Inpatient)	1 (Inpatient)
Two weeks after start of Intervention	1 (Inpatient)	NIL	NIL
Post-Intervention	1 (In/ Outpatient)	NIL	1 (In/ Outpatient)
One Month Post-Intervention	1 (Outpatient)	NIL	NIL
Three Months Post-Intervention	1 (Outpatient)	NIL	1 (Outpatient)

SURE program intervention will start after pre-intervention TMS screening, clinical assessment and fMRI investigations. It consists of 4 weeks of additional 1 hour daily self-exercise and functional use of affected UL in the hospital ward 6 days a week. The subjects will require to wear an accelerometer on unaffected wrist for 3 weekdays of first week to establish baseline of use, and wear an accelerometer on affected wrist 3 weekdays (8am -8pm each day) per week so that the actual affected UL use can be feedback to subjects during review. Please see attached file: Patient's_Involvement_In_Study_15_April_2017 for summary of each subject's involvement in the study.

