6. METHODS AND ASSESSMENTS

Outcome Measures

UL functional outcome measures

UL Fugl Meyer Scale (ULFM)

UL Fugl Meyer Scale will be used to stratify subjects to their level of UL severity and assessment of UL impairment. ULFM score can be subdivided into 3 categories to define the different level of severity of paresis (severe= 0 to 22; moderate=23 to 50; mild>= 51). ULFM will be one of the primary outcome measures to determine UL recovery.

Action Research Arm Test (ARAT)

ARAT will be used as the primary outcome measure of UL functional outcome. ARAT will be one of the primary outcome measures to determine UL recovery.

Measure of UL practice and use

Rating of Everyday Arm-use in the Community and Home (REACH Scale)

The REACH scale is a self-report measure that captures how much an individual with stroke use affected UL outside clinical setting. It has one scale for subjects whose dominant UL is affected and another scale for subjects whose non-dominant UL is affected. It will be used to rate patients' affected UL use after discharge.

Measure of UL practice and use using accelerometry

One tri-axial accelerometer (ActiGraph GT3X+, ActiGraph LLC, Pensacola, Florida) will be placed on subject's unaffected wrist to establish the duration of unaffected UL use in the ward for 3 days in the first week. Another tri-axial accelerometer will be placed on subject's affected wrist for 3 weekdays each week of the 4-week intervention period to assess the amount of affected UL use. The accelerometers will be worn by all subjects (both experimental and control groups) from 8am to 8 pm on the day of donning.

Measures of feasibility of accelerometry in measuring affected UL use

The compliance rate of wearing the accelerometers during the 4 weeks of intervention period will be used to assess compliance. Subjects will also be asked to fill a questionnaire to rate the acceptance, ease, comfort, discomfort, benefits, and problems of wearing the accelerometers in the ward.

*Measures of **SURE** program's feasibility*

The key measure of **SURE** program's feasibility will be the additional affected UL practice and use per day as measured by the accelerometers.

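### The key accelerometer comparison uses affected-arm use per day, unscaled for time worn, so any wear difference between groups would be read as a difference in practice

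*Protocol*

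**What the plan says.** **The comparison.** Section 11.2, under the analysis of the program's feasibility, lists "The differences in the duration of affected UL use per day" and, in the same sentence, "the ratio of affected UL use/ non-affected UL use between the experimental group and control group (from the accelerometer recordings". Neither is expressed per hour worn.

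**Its role.** Section 6 states that the key measure of feasibility "will be the additional affected UL practice and use per day as measured by the accelerometers". More practice in the ward is also the first half of hypothesis 1 (Section 2.1) and part of the primary objective (Section 2.2).

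**The wear schedule.** Section 6: "The accelerometers will be worn by all subjects (both experimental and control groups) from 8am to 8 pm on the day of donning". The affected-arm device goes on the "subject's affected wrist for 3 weekdays each week of the 4-week intervention period to assess the amount of affected UL use". The unaffected wrist is monitored for three days in week 1 only (Sections 4 and 6).

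**Wear compliance.** Section 6: "The compliance rate of wearing the accelerometers during the 4 weeks of intervention period will be used to assess compliance". Section 11.2 uses it to judge whether accelerometers are feasible and acceptable. It is not linked to the arm-use comparison.

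**Feedback.** Section 1.1 presents accelerometer monitoring and feedback as a component of SURE. Section 4, in the paragraph on the SURE intervention, says the affected wrist is monitored "so that the actual affected UL use can be feedback to subjects during review". Section 5 describes home review of arm use after discharge in the experimental-group text. The control-group text describes reviews of the education booklet only.

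**The concern.** Recorded use per day is the product of two things: how much the arm moves per hour of wear, and how many hours the device is on. Only the first is practice. The protocol foresees that the second will vary, since it plans a compliance rate and a questionnaire on discomfort and problems with the device, yet the stated comparison does not separate the two.

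This would matter little if wear were sure to be alike in both groups. There is a plausible reason why it might not be. In the SURE group the reading is part of the intervention and is discussed with the subject; nothing similar is described for controls, who have less reason to keep the device on. At stake is the key feasibility conclusion, that SURE adds affected-arm practice. With 10 subjects per group (Section 11.1), a few poor wearers could move the group difference noticeably.

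**Working it through.** **1. The plan's own dose figure.** Section 8.1 gives 24 additional hours: 60 min × 6 days × 4 weeks = 1,440 min = 24 h. It reproduces, so 60 min/day is used below as the yardstick. The sample size is a feasibility choice, with no power calculation to reproduce.

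**2. Scheduled wear (Section 6).**
- Affected wrist: 12 h × 3 days × 4 weeks = 144 h per subject.
- Unaffected wrist: 12 h × 3 days = 36 h, all in week 1.

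**3. Effect of a wear gap when true practice is equal.** Let r be use in min per hour worn, the same in both groups, and let w be the fraction of the 12 h actually worn.

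Spurious difference = 12 × r × (w in SURE − w in control)

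The 12 h comes from the protocol. The values of r and the wear gap are assumptions; the protocol gives neither. Each cell shows min/day, with the percentage of 60 min in brackets.

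| r (min/h) | gap 5 points | gap 10 points | gap 15 points |
|---|---|---|---|
| 5 | 3 (5%) | 6 (10%) | 9 (15%) |
| 10 | 6 (10%) | 12 (20%) | 18 (30%) |
| 15 | 9 (15%) | 18 (30%) | 27 (45%) |

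For example, 95% against 80% wear at 10 min/h gives 12 × 10 × 0.15 = 18 min/day. With equal wear every cell is 0. If controls wore the device more, the sign would reverse and real extra practice would be hidden.

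**4. The same data per hour worn.** (12 × r × w) / (12 × w) = r in each group, so the difference is 0 at any wear level.

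**5. Whether the ratio already deals with this.** In week 1, if both wrists are worn for the same hours, w cancels from numerator and denominator. In weeks 2 to 4 only the affected wrist is monitored, so the denominator can only come from week 1 and w stays in the numerator. With equal week-1 denominators and equal hourly use, the SURE ratio exceeds the control ratio by the factor w in SURE / w in control:
- 0.95/0.90 = 1.06, or 6% higher.
- 0.95/0.80 = 1.19, or 19% higher.

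The ratio therefore gives no protection after week 1.

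**6. Where per-hour scaling misleads.** Suppose a subject uses the arm for 120 min in 12 h, which is 10 min/h. If the device comes off for 2 idle hours, the daily duration is still 120 min, but use per hour worn becomes 120/10 = 12 min/h, 20% too high. Neither measure is safe alone.

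**The case against.** The strongest reply is that handling of non-wear (detection rules, minimum valid days, averaging over days) is normally left to a statistical analysis plan or a device-processing manual, and that plan is not shown. That stands for those rules, and their absence is no finding here. It does not cover the measure itself: the protocol names an unscaled daily duration, and an analysis plan that followed it would inherit the problem.

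Second, the wear window is the same 12 h in both groups, and the review visits have the same frequency (Section 5). Both facts are correct and make a large gap less likely. But a common schedule is not a record of common wear.

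Third, this is a small exploratory pilot, and Section 11.2 says only that these differences will be calculated. That limits the consequences, though not the direction of the reasoning.

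Several stronger readings are tempting and are not supported:
- *Wear will differ by group.* No section says so; it is a possibility.
- *Controls receive no device feedback.* This is an inference from where the feedback is described. The protocol never says it.
- *This is the only objective test of hypothesis 1.* That hypothesis also covers functional outcome, assessed with ULFM and ARAT by a blinded assessor. The point concerns the practice component only.
- *The 8pm limit cuts off the evening exercise.* Section 5 has the exercise "distributed across morning, afternoon, and evening per day for 6 days per week", but gives no clock time for the evening. Extending wear for late sessions would also lengthen it in SURE alone.

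**Conclusion.** The point holds in a limited form. The key feasibility comparison is stated as affected-arm use per day without scaling to time worn, and the accompanying ratio does not correct for wear after week 1. If wear differs between groups, that difference cannot be told apart from a difference in practice.

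Under the assumed inputs the artefact is 3 to 27 min/day, or 5% to 45% of the 60-minute daily prescription. It is zero if wear is equal. Hourly use, the size of the wear gap and its direction are all assumptions, so the figures show sensitivity and do not predict a bias. The trial is not invalidated; the correction is worth making because the measure carries the main feasibility claim and the remedy is cheap.

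**What to change.** In Section 11.2, under the analysis of the program's feasibility:

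- Compare the groups on affected-arm use per hour worn, beside the daily duration already named. Average the monitored days to one value per subject and give the group difference with a 95% CI for each measure.
- Tabulate hours worn per scheduled day by group, so that a reader can see whether the two measures should agree.
- Take wear time from the wear records that supply the compliance rate. It should not be inferred from absence of movement, because a paretic arm lying still would then be counted as non-wear.

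The cost is some extra analysis and one more table, with no new device or visit. The protocol does not say how finely wear is recorded; if only days are noted, on and off times would have to be added. Per-hour use can itself mislead when devices come off mainly during idle time, which is why the daily duration should stay beside it. With 10 subjects per group the intervals will probably be wide, which is a fair description of what this pilot can show.
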